3.1.3 Consolidation treatment phase (2 cycles of chemotherapy plus immunotherapy)

- 1 Envafolimab: 200mg, subcutaneous injection, Q2W, 2 cycles, administered simultaneously on the first day of chemotherapy.
- 2 mFOLFOX6: Q2W, 2 cycles: oxaliplatin 85mg / m² intravenous infusion for 2h, day 1. Linovorin calcium 400mg / m² was infusion for 2h on day 1. Fluoruracil 400mg / m²,

day 1, then $1200\text{mg} / (\text{m}^2 \cdot \text{d})$ 2d, continuous intravenous infusion (total $2400\text{mg} / \text{m}^2$, 46 to 48 h).

3.2 Surgical treatment protocol

Time to surgery: 6 weeks after completion of last neoadjuvant radiotherapy / 3 weeks after consolidation immunotherapy.

Surgical method: According to the surgical principle of total mesorectal resection (TME), the specific procedure is decided by the surgeon according to the center team.

3.3 Postoperative adjuvant treatment regimen

The postoperative treatment regimen includes adjuvant chemotherapy or waiting observation strategy, which will be discussed by the investigator team. Postoperative adjuvant chemotherapy regimen: starting about 3 weeks after R0 resection, 2 cycles of mFOLFOX6 regimen, and about 6 months of perioperative treatment. For patients who failed to receive preoperative treatment, determine whether to change the treatment regimen based on the discussion results of the MDT team.

[figure not shown]

Figure. Study flow chart of TNT with PD-L1 in MSS LARC

The flow of the study is shown below:

3.4 The Watch Wait policy

A "watchful wait" strategy (non-radical surgery) for patients whose tumor withdrawal achieved clinical complete remission (cCR) (watch-and-wait policy). Specific strategies include: digital rectal examination, tumor markers every 1 to 2 months for 2 years, thoracic, abdominal and pelvic CT, pelvic MRI, endorectal ultrasound, colonoscopy and biopsy, and even PET-CT every 3 months.

3.5 therapeutic review

1 Effectiveness: objective efficacy evaluation according to RECIST1.1 standard evaluation, divided into CR, PR, SD and PD (see 4.7 for details);

After the end of induction therapy (available), after the completion of concurrent chemoradiotherapy (available), after the end of consolidation therapy / before surgery (required) can be evaluated after neoadjuvant treatment, according to the following conditions:

- 1) The patient evaluation is CR: if anal preservation surgery is feasible, direct surgical resection; if anal preservation is impossible, after full communication and informed consent, wait for observation (wait and watch);
- 2) Patients were evaluated as PR or SD, with direct surgical resection;
- 3) The patient was evaluated as PD, but there was still possible R0 resection in preoperative evaluation, and surgical resection was performed;
- 4) If the patient is evaluated as PD and cannot be removed by R0, the replacement treatment plan should be discussed according to MDT;
- 5) If distant metastases during neoadjuvant therapy are treated in accordance with the guidelines for diagnosis and treatment of metastatic colorectal cancer.

* After completion of neoadjuvant therapy, patients must receive efficacy evaluation of the same means in the same center.

2 Surgical resection rate: R0, R1, R2 (R0 no residual tumor; R1 microscopic tumor residue; R2 gross tumor residue);

3 Safety: Observation and graded according to NCI CTC AE 5.0 toxicity criteria. Tumor markers, blood routine, blood biochemistry, and liver and kidney function were checked every 2 weeks. In the course of treatment, the occurrence of adverse reactions should be closely monitored, including edema, gastrointestinal reaction, leukopenia, anemia, hand and foot syndrome, rash, muscle spasm, diarrhea, etc., and the time,

degree, treatment methods and treatment results of adverse reactions should be recorded.

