Using computer (SPSS or R) software package, count data adoption rate, mean and 95% credible interval for measurement data; t-test for measurement data when comparing two groups, chi-square test for count data, Kaplan-Meier and Log Rank methods for survival analysis, and Cox proportional risk model for prognosis analysis. The probability P-value was used at any stage, and the statistical significant difference bound was used at 0.05.

Safety analysis: The toxicity evaluation criteria were evaluated according to the NCI-CTC 5.0 criteria. Specific statistical methods are the same as above.

Type of analysis

Prior to database lock, the following three datasets were identified.

The primary efficacy analysis will be performed in all enrolled populations (the intent-to-treat population or the ITT population) and the per-protocol population (PP). Secondary efficacy analysis and exploratory analysis will be performed in the intention-to-treat population. Non-inferiority analysis will be performed in the per-protocol population.

1. Intention-to-treat population

The intention-to-treat population consists of all patients randomized to any of the two treatment arms. Analysis will be performed according to the treatment groups randomassigned by the patients.

2. Population conforming to the protocol

Patients who have not received any dose of chemotherapy or chemoradiotherapy, or those who have suffered a serious violation of the inclusion or exclusion criteria. Analysis will be performed according to the treatment groups randomassigned by the patients.

3. Safety population

The safety population includes all patients who have received at least one dose of chemotherapy or radiotherapy. The Safety population was used to analyze all safety parameters. Patients were assigned to the treatment group based on the medication they actually received.

4. The data that should be excluded during the analysis

There were no excluded data available.

Medium-term analysis

An interim analysis of the efficacy endpoints is not performed in this study. An independent data security monitoring team will monitor the safety data throughout the study. All safety data descriptive analysis will be performed after study treatment for all patients enrolled in this study. This analysis will be strictly limited to the safety data and will not include any efficacy endpoints.

4. research contents

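### The primary endpoint needs a surgical specimen, the plan lets some patients go without surgery, and no text says how they count for pCR

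*Combined protocol and SAP*

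**What the plan says.** **Endpoint.** Section 4.1 bases the sample size on postoperative pCR: 15% under conventional treatment, 35% expected, alpha 0.05, power 80%, 10% loss, 35 patients. The Protocol summary (statistical method, item 2) has two pathologists judge pCR. Section 4.7 item 3 refers only to postoperative specimens. Clinical complete response is a separate secondary endpoint (section 2.2).

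**Routes without a specimen.**
- Section 3.4: watch-and-wait as a "strategy (non-radical surgery) for patients whose tumor withdrawal achieved clinical complete remission (cCR").
- Section 3.5 item 1, for patients rated CR: resection where the anus can be preserved; otherwise "if anal preservation is impossible, after full communication and informed consent, wait for observation (wait and watch").
- Section 3.5 item 4: "If the patient is evaluated as PD and cannot be removed by R0, the replacement treatment plan should be discussed according to MDT".
- Section 3.5 item 5: "If distant metastases during neoadjuvant therapy are treated in accordance with the guidelines for diagnosis and treatment of metastatic colorectal cancer".

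**Analysis populations (section 3.10).** "The primary efficacy analysis will be performed in all enrolled populations (the intent-to-treat population or the ITT population"), and the same sentence goes on to name the per-protocol population as well. The definitions follow:
- ITT: "The intention-to-treat population consists of all patients randomized to any of the two treatment arms".
- Per-protocol: "Patients who have not received any dose of chemotherapy or chemoradiotherapy, or those who have suffered a serious violation" of the eligibility criteria.
- Excluded data: "There were no excluded data available".

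The Protocol summary uses other names, FAS and PPS, and does not define them.

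**The concern.** A patient who is watched, or who progresses and is not resected, has no specimen and so no pCR value. Three treatments are possible: non-pCR, excluded, or (for a watched complete responder) counted as a response. The plan chooses none of them.

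The choice acts in a known direction. If most watched patients are truly free of tumour, scoring them non-pCR or dropping them lowers the observed rate. Scoring them as responders raises it, and so does dropping unresected patients with progression. In an uncontrolled trial of 35, a rule settled after the data are seen would leave a result near the boundary open to question.

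The number of patients affected is uncertain too, because sections 3.4 and 3.5 word entry to watch-and-wait differently.

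**Working it through.** **1. The plan's sample size.** Inputs from section 4.1: p0 = 0.15, p1 = 0.35, alpha 0.05, power 80%, 10% loss. Sidedness is not stated. One-sample normal approximation:

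n = [(z_alpha × √(p0(1−p0)) + z_power × √(p1(1−p1))) / (p1−p0)]²

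- Two-sided 0.05: [(0.6998 + 0.4014)/0.20]² = 30.3, so 31; 31/0.9 = 34.4, so 35. This matches.
- One-sided 0.05: [(0.5873 + 0.4014)/0.20]² = 24.4, so 25; 25/0.9 = 27.8, so 28. No match.

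Of the variants tried, only two-sided 0.05 gives 35, so one-sided 0.025 is the main setting below. The loss allowance covers 35 − 31 = 4 patients.

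**2. Cut-offs, assuming an exact binomial test against 15%.** The plan names no test for pCR.
- One-sided 0.025: at least 11 of 35 (p = 0.0110; 10 of 35 gives 0.0292). Power at 35% is 72.8%.
- One-sided 0.05: at least 10 of 35 (p = 0.0292; 9 of 35 gives 0.0689). Power is 83.5%.

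**3. One data set, three answers.** 10 pCR among 34 operated patients, 1 watched:
- as non-pCR, 10/35: p = 0.029
- excluded, 10/34: p = 0.024
- as responder, 11/35: p = 0.011

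The difference between the first two comes from the discrete cut-off, which is 10 at n = 34 and 11 at n = 35.

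**4. How often the rule matters.** Let k patients be watched, a share f of them truly pCR, with a true overall rate of 35% (12.25 of 35). The rate among operated patients is q = (12.25 − f×k)/(35 − k), and X ~ Binomial(35 − k, q).
- Power, non-pCR rule: P(X ≥ 11)
- Power, excluded: P(X ≥ 10), the cut-off at n = 34, 33 and 31
- Power, responder rule: P(X ≥ 11 − k)
- Opposite decisions, responder versus non-pCR: P(11 − k ≤ X ≤ 10)

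Worked case, k = 2 and f = 1: q = 10.25/33 = 0.311; P(X ≥ 11) = 0.453; P(X ≥ 9) = 0.740; difference 0.287.

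One-sided 0.025, ranges for f = 0.5 to 1:

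| Watched | Power, non-pCR | Power, excluded | Power, responder | Opposite decisions |
|---|---|---|---|---|
| 1 | 67-60% | 79-73% | 79-73% | 12-13% |
| 2 | 60-45% | 74-60% | 84-74% | 24-29% |
| 4 | 45-18% | 60-30% | 93-76% | 47-58% |

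At one-sided 0.05 (cut-off 10), power under the non-pCR rule falls from 83% to 79-73% (1 watched) or 74-60% (2 watched).

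**5. False positives under the responder rule.** True rate 15%: P(X ≥ 11 − k) with n = 35 − k and rate (5.25 − f×k)/(35 − k). At f = 0.5 this gives 1.5% (k = 1) and 2.1% (k = 2), both below 2.5%. At f = 1 it is lower still.

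**6. Where it does not matter.** With 11 or more pCR among operated patients, the 35-patient cut-off is met even when everyone else counts as non-pCR. Exclusion or responder scoring only adds to that, so all rules agree. The design expects 0.35 × 35 = 12.25 pCR.

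**The case against.** **Section 3.10 already points to all enrolled patients.** A reader might infer that non-pCR scoring is therefore implied. The text does not carry that. The same sentence names the per-protocol population without ranking the two. The ITT definition relies on randomisation to two arms that do not exist here. The remark on excluded data sets no rule. A denominator also does not give an outcome value to a patient without a specimen. The 10% loss allowance is not a counting rule either and, if anything, suggests an evaluable denominator.

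**Few patients will be watched.** The background cites 100% sphincter preservation in another trial, but among 12 patients who had surgery. That cannot show how many avoid it. The numbers used here are assumptions and nothing more.

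**The trial is exploratory and mostly descriptive, so there is no decision to reverse.** This stands in part. No test for pCR is named, and the cut-offs above are conditional on the exact test. But section 4.1 sizes the trial on 15% versus 35%, and section 3.10 sets a 0.05 threshold.

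**Sections 3.4 and 3.5 may not conflict.** This largely stands. Item 1 of section 3.5 can be read as narrowing section 3.4. A reader might infer a flat contradiction, but the documents show only two different wordings with no cross-reference. The study flow chart is not available to this review and may show the branch.

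**Conclusion.** The gap is real and should be fixed. pCR needs a specimen, the plan provides routes without one, and the population definitions in section 3.10 are wrong for this trial and leave the counting open.

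The size is conditional on an exact test at one-sided 0.025, a true rate of 35%, and 50-100% of watched patients being truly pCR. On those terms the responder and non-pCR rules disagree in about one trial in eight with 1 watched, about a quarter with 2, and about half with 4.

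Two stronger readings are not supported. A reader might infer that the missing rule inflates false positives; at one-sided 0.025 with 1 or 2 watched, the responder rule stays at or below 2.1%. A reader might also blame the shortfall from 80% power on watch-and-wait; under the exact test, power is already 73% with nobody watched. The sample size of 35 itself reproduces and is not in question.

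**What to change.** 1. In section 3.10, replace the two-arm ITT text with all enrolled patients, correct the per-protocol definition, and use one set of population names there and in the Protocol summary. Name the all-enrolled analysis as decisive and per-protocol as supportive.
2. State that any patient without a surgical specimen, for whatever reason, counts as non-pCR in the primary analysis. This is a conservative choice made here, not one the plan already implies.
3. Pre-specify two supportive analyses: pCR among operated patients only, and, over all enrolled, pCR plus clinical complete response sustained to a time the sponsor names. Report the number watched.
4. Reconcile or cross-reference sections 3.4 and 3.5 on who enters watch-and-wait. This review does not choose the clinical rule.

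**Cost.** Wording only, with no new visits. The primary rate and the power become less favourable. Keep 35 patients and restate the power: at one-sided 0.025 under an exact test, 73% with nobody watched, and lower with each patient watched, as tabulated above.

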3.6 Dose adjustment and adverse reaction treatment

Hematological toxicity dose adjustment

All dose changes should be documented and treated with the most adequate supportive therapy. If the symptoms resolve immediately after supportive care and continued study treatment is considered appropriate and the investigator believes the treatment is beneficial to the patient, consider continuing the same dose of study treatment plus appropriate continued supportive care. If the reduction is medically required, the reduction of chemotherapy is allowed. Adjust this cycle dose according to the lowest blood count after last dose (refer to the table below):

low		The next cycle dose
Neutrophil number (10 ⁹ / L)	Platelet count (10 ⁹ / L)	
≥0.5	And oneself 50	invariant
<0.5	Or <50	The subsequent dose of chemotherapy will be reduced by 20% at the discretion of the investigator

After two reductions, another 4 degrees of neutropenia or III degree grain deficiency with fever (> 38.5°C) or above 3 degrees occurred, without the third reduction, the investigator will discuss whether to continue the trial according to the specific situation.

Non-hematologic toxicity including diarrhea, dermatitis, myxitis mucositis and peripheral neuritis

For non-haematological toxicity (except vomiting and alopecia), the subsequent dose of chemotherapy should be reduced by 20% at the discretion of the investigator;

Peripheripheral nerve toxicity above 3 degrees was reduced by 20% at the discretion of the investigator. If the peripheral nerve toxicity does not decrease or continues to worsen, the investigator will discuss whether to continue using oxaliplatin in adjuvant chemotherapy according to the specific situation.

hepatotoxicity

- Bilirubin: If the bilirubin levels are abnormal in the study, the next cycle should be delayed. If 4 weeks, the trial;
- Liver enzymes: AST and / or ALT and / or alkaline phosphatase levels abnormal in the absence of disease progression, liver protection treatment, within 2 weeks, not returning to normal, dose can be adjusted according to the table below.

If the liver function recovers in the next cycle, the dose should be increased to the previous level.

AST/ALT price	Alkaline phosphatase values	dose titration
<1.5×ULN	<5×ULN	No dose adjustment is required
> 1.5 ULN to <2.5 ULN	<2.5×ULN	No dose adjustment is required
2.5 ULN to <5 ULN	<2.5×ULN	Subsequent dose reduction of chemotherapy was 20-25% as determined by the investigator
> 1.5 ULN to <5 ULN	>2.5×ULN <5×ULN	
> 5 ULN and / or > 5 ULN		Delay by up to two weeks, if still not Recovery, at the discretion of the investigator, Ill Whether the person withdrew from the study.

Immune-related adverse effects

Based on the mechanism of action, patients receiving its treatment may develop immune-related adverse reactions, including severe and fatal cases. Most immune-related adverse effects are reversible and can be managed by suspension or cessation of the treatment and administering corticosteroid therapy and / or supportive therapy. Depending on individual patient safety and tolerability, dose suspension or permanent discontinuation may be required. Increase or dose reduction is not recommended. See the table below for recommended envafolimab.

As recommended for envafolimab

Immune-related adverse effects	order of severity ‡	Treatment adjustment protocol
pneumonia	Level 2	Sucontinue until adverse effects return to grade 0-1

	Grade 3 or 4 or recurrent grade 2	Permanent withdrawal of drugs
Diarrhea and colitis	Level 2 or 3	Sucontinue until adverse effects return to grade 0-1
	Level 4	Permanent withdrawal of drugs
hepatitis	Grade 2, aspartate aminotransferase (AST) or alanine aminotransferase (ALT)> 3 to 5 times the upper limit of normal (ULN); and / or total bilirubin (TBIL)> 1.5 to 3 times ULN	Suuse until adverse effects return to grade 0-1 and prednisone 10mg / day or equivalent dose
	Grade 3, AST or ALT> 5 x ULN, and / or TBIL> 3 x ULN	Permanent withdrawal of drugs
Nephritis and renal dysfunction	Grade 2, creatinine> 2-3 times ULN	Sucontinue until adverse effects return to grade 0-1
	Grade 3, creatinine> 3 times ULN or> 4.0 mg/dL, with indication for hospitalization; life-threatening, indication for dialysis treatment	Permanent withdrawal of drugs
endocrine disease	Grade 2 hyperthyroidism	Suspension until symptom improvement or adverse response remission to grade 0-1
	Grade 2 hypothyroidism	Continue the medication, by standard therapy, by hormone replacement therapy ^a Control
	Grade 2 hyperglycaemia or type 1 diabetes mellitus	Suuse until adverse reactions return to grade 0-1. Start insulin replacement therapy as clinically indicated, and use hypoglycemic drugs for hyperglycemia
	Grade 2 pituitary inflammation	Suused until the subject is clinically stable

	Grade 3 or 4 hypophysitis	Suspend until hormone replacement therapy ^a To when the subject was clinically stable
	Grade 2 adrenal insufficiency	Stop until the subject is clinically stable
Skin adverse effects	Grade 3, or suspected Stevens-Johnson syndrome (Stevens Johnson syndrome, SJS) or toxic epidermal necrolysis (Toxic Epidermal Necrolysis, TEN)	Continue until adverse effects return to grade 0-1
	Level 4, or to confirm the SJS or TEN	Permanent withdrawal of drugs
Carditis	Level 1	Suspension of dosing
	Adventitia level 2	Permanent withdrawal of drugs
Thrombocytopenia	Level 3	Continue until adverse effects return to grade 0-1
	Level 4	Permanent withdrawal of drugs
Other immune-related adverse effects	Grade 1 encephalitis Grade 2 or 3 pancreatitis Grade 2 myasthenia gravis Grade 3 or 4 with elevated blood amylase or elevated lipase Other immune-related adverse reactions that first occurred in grade 2 or 3 include dermatitis, etc	The administration should be suspended until the adverse reaction returns to grade 0-1, and the encephalitis should decide whether to continue the medication based on clinical judgment
	Adventitia grade 2 encephalitis Grade 4 pancreatitis Grade 3 or 4 myasthenia gravis	Permanent withdrawal of drugs

	Guillain Barre Syndrome (Guillain-Barre syndrome, GBS) Other immune-related adverse reactions first occurring in grade 4 include dermatitis	
Recurrent or persistent adverse effects	Recurrent Grade 3 or Grade 4 (except for endocrine disorders) Within 12 weeks after the last dose: Grade 2 or 3 adverse effects did not improve to Grade 0-1 (except endocrine disease) or the corticosteroid dose was not reduced to prednisone 10mg daily, or equivalent dose	Permanent withdrawal of drugs
Injection site reaction	Level 2	cont.rem
	Level 3-4	Permanent withdrawal of drugs
hypersensitivity	Level 2	Stop the drug administration immediately. Depending on the observed intensity of response, antihistamines should be given in advance in the next cycle of treatment and the subcutaneous injection is slowed.
	Level 3-4	Immediately continue immediately with subsequent permanent withdrawal

Toxicity grading was determined using the National Cancer Institute Common Terminology Assessment Criteria for Adverse Events version 4.03 (NCICTCAE v4.03).

^aFor advice on hormone replacement therapy, see the envafolimab insert [Notes].

Adverse reactions related to radiotherapy

Gastrointestinal reaction: nausea, vomiting and other gastrointestinal reaction after radiotherapy, can be antivomiting, promote gastrointestinal peristalsis drug treatment;

Bone marrow suppression: if white blood cells, red blood cells and platelets decrease after radiotherapy, the recombinant human granulocyte colony stimulating factor, recombinant human thrombopoietin, blood transfusion and other treatments can be given accordingly;

Radioactive dermatitis: after radiotherapy, the perianal skin appears itching, erythema, ulcer and other symptoms, and the skin protective agent can be applied;

Radioactive proctitis: after radiotherapy, abdominal pain and diarrhea, emergency, hematochezia and other symptoms, can be spastic, diarrhea, antidiarrhea, sitting basin, dexamethasone enema treatment;

Tumor hemorrhage: tumor rupture after radiotherapy, causing massive bleeding of blood vessels, endoscopic hemostasis or interventional embolization should be performed in emergency department, and radiotherapy should be terminated.

Treatment of the adverse reactions

The treatment of other adverse reactions can refer to the drug instructions or the routine treatment principles of the test center.

3.7 fl.up

1) Before treatment

All patients participating in this trial should sign an informed consent form and receive a copy of the informed consent form. If the patient agrees to participate in the trial, the participation form should be completed and signed immediately, and thereafter the patient can be enrolled. Within 28 days prior to initiation of treatment, the investigator should evaluate the following clinical and laboratory indicators.

- 1 Past history, including: age, sex, tumor location, disease stage, histological stage, history of perforation or obstruction, duration of surgery, and the procedure
- 2 Physical strength status score (see Appendix)
- 3 Clinical examination, height (pre-treatment measurement only), body weight
- 4 electrocardiogram
- 5 Collection of clinical laboratory data:

Routine blood indicators: hemoglobin, white blood cells, platelets and neutrophils;
Blood biochemical indexes: creatinine, alkaline phosphatase, total bilirubin, SGOT,

SGPT;

Coagulation function: prothrombin time (PT), activated partial thromboplastin time (APTT) and international standardized ratio (INR);

Thyroid function: thyroid-stimulating hormone (TSH), free T3, free T4;

Urine routine: including urine specific gravity, pH value, white blood cells, red blood cells, protein, glucose, ketone body, and tube type. Two consecutive routine urine testing of urine protein + +, it is recommended to test 24 hours of urine protein quantification as soon as possible (such as within 72 hours);

Subactive blood examination;

HIV check;

HBV infection: including hepatitis B five and HBV DNA;

HCV-infected persons: including HCV RNA.

6 Detection of tumor markers: CEA

7 Enteroscopy and pathological diagnosis

8 Enhanced CT scans of the chest, abdominal, and pelvic areas

9 Abdominal B ultrasound

10 pelvic cavity MRI

11 Ctoluminal ultrasound

12 Genetic testing: MSI status (or MMR status assessed by immunohistochemistry),
POLE / POLD 1, PTEN mutation status, TMB status, RAS and BRAF gene mutation testing

13 Peripheral tumor blood: CD3 +, CD4 +, and CD8 + T cell

14 Concomitant medication: collect medication within the 3 months before treatment

15 Quality of life assessment

Note: The relevant examinations involved in this institute were conducted by the Department of Clinical Laboratory of Yunnan Cancer Hospital, Department of Pathology, Department of Cardiac function, Gastroenteroscopy room, molecular Diagnosis Center and Yunnan Cancer Institute;

2) During the treatment process

During the treatment process, the investigator may increase the follow-up content or increase the frequency of follow-up as needed. The treatment-phase follow-up program needs to be completed before each cycle of treatment.

The follow-up content of the trial plan is as follows:

1 Body weight: during induction treatment, synchronous treatment, consolidation treatment, before and after surgery

- 2 Physical examination: performed during induction treatment, during synchronous treatment, during consolidation treatment, and before and after surgery
- 3 ECOG PS Score: during induction treatment, during synchronous treatment, during consolidation treatment, and before and after surgery
- 4 12-lead ECG: performed during induction treatment, during synchronous treatment, during consolidation treatment, and before and after surgery
- 5 Blood routine: during induction treatment, synchronous treatment, consolidation treatment, before and after surgery
- 6 Blood biochemistry: during induction treatment, during synchronous treatment, during consolidation treatment, before and after surgery
- 7 Detection of tumor markers: during induction treatment, during synchronous treatment, during consolidation treatment, and before and after surgery
- 8 Thyroid function: after the end of induction therapy / before synchronous chemoradiotherapy, after completion / before consolidation therapy and before surgery
- 9 Peripheral blood test: after induction treatment / before synchronous chemoradiotherapy, after synchronous chemoradiotherapy / before consolidation treatment, before and after surgery
- 10 Enhanced CT scans of chest, abdominal and pelvic areas: after completion of induction therapy / before concurrent chemoradiotherapy, after completion of concurrent chemoradiotherapy / before consolidation therapy, and before and after surgery
- 11 Pelvic MRI: after completion of induction therapy / before concurrent chemoradiotherapy, after completion of concurrent chemoradiotherapy / before consolidation therapy
- 12 Adverse events: Adverse events after initiation of treatment.
- 13 Concomitant medication: Continuous collection.
- 14 Quality of life assessment: collected per cycle

3) After the completion of the treatment

After completion of treatment, patients should be reviewed at the items and time in the table below; until tumor recurrence or at least 2 years. Review beyond the time of the following table can be conducted according to the habits of different centers, with PET / CT if necessary.

project	After the first moon								
	1	3	6	9	12	15	18	21	24
/	/	/	/	/	/	/	/	/	/
symptom	✓	✓	✓	✓	✓	✓	✓	✓	✓
check-up	✓	✓	✓	✓	✓	✓	✓	✓	✓
routine blood test	✓	✓	✓	✓	✓	✓	✓	✓	✓
Blood biochemical	✓	✓	✓	✓	✓	✓	✓	✓	✓
CEA	✓	✓	✓	✓	✓	✓	✓	✓	✓
Peripheral blood detection	✓								
Chest / abdominal / pelvic CT	✓	✓	✓	✓	✓	✓	✓	✓	✓
colonoscope *					✓				✓
Assessment of QoL	✓	✓	✓	✓	✓	✓	✓	✓	✓
Observe the efficacy	✓	✓	✓	✓	✓	✓	✓	✓	✓

* If the lesion is found by colonoscopy, the colonoscopy period can be shortened according to the specific situation.

4) Safety follow-up

Safety follow-up was performed 28 days after the last dose and the trial planned follow-up is as follows:

- 1 weight
- 2 check-up
- 3 ECOG PS Score
- 4 And a 12-lead ECG
- 5 routine blood test
- 6 Blood biochemical
- 7 routine urine test
- 8 coagulation function
- 9 thyroid function
- 10 Enhanced thoracic, abdominal, and pelvic CT scans: Patients who are discontinued due to disease progression do not need further follow-up enhancement

- 11 Adverse events: Continuous follow-up until adverse event recovery or further observation is not required by the investigator.
- 12 Concomitant medication: Continuous collection until treatment for the adverse event is completed or the investigator.
- 13 Quality of life assessment

5) Survival follow-up

After disease progression, patient survival status was collected every 3 months allowing telephone follow-up.

5) Patient compliance observation

The investigator's responsibility to ensure patient compliance with the trial will be examined by itinerant representatives.

3.8 data collection

All data shall be timely, truthfully and detailed in the medical record register (Case Report Form, CRF) or CRF software. The medical record form should be filled in by special personnel and signed by the project leader. The medical records (CRFs) shall be checked and collected regularly, and recorded according to the time node required by the clinical trial management center of the hospital.

After the clinical trial, the unit shall write the clinical summary report according to the standard requirements.

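### In the section 3.6 envafolimab table, two rows (grade 3 skin reactions or suspected SJS/TEN, and level 3 thrombocytopenia) say to continue dosing where the context calls for suspension

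*Combined protocol and SAP*

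**What the plan says.** Section 3.6 introduces the table by saying that most immune-related reactions can be handled by suspending or stopping treatment, with corticosteroids or supportive care. It adds: "Depending on individual patient safety and tolerability, dose suspension or permanent discontinuation may be required", and "Increase or dose reduction is not recommended".

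The table then gives an action for each reaction and severity. For skin reactions of grade 3 or suspected SJS or TEN, and again for thrombocytopenia of level 3, the action is "Continue until adverse effects return to grade 0-1". The next step in both categories (level 4, or confirmed SJS or TEN) is permanent withdrawal.

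Other rows of the same table:

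- Pneumonia level 2, diarrhea and colitis level 2 or 3, and nephritis grade 2: "Sucontinue until adverse effects return to grade 0-1".
- Other immune-related reactions first occurring at grade 2 or 3, with dermatitis named: "The administration should be suspended until the adverse reaction returns to grade 0-1".
- Grade 2 hypothyroidism: "Continue the medication, by standard therapy", with hormone replacement.
- Hypersensitivity level 2: "Stop the drug administration immediately". Hypersensitivity level 3-4: "Immediately continue immediately with subsequent permanent withdrawal".

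**The concern.** The two cells tell the investigator to keep giving envafolimab while a serious toxicity is present. Because the plan advises against changing the dose, holding or giving the drug is the only control on envafolimab exposure short of permanent withdrawal. A reversed hold instruction therefore removes that control for these two events.

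The garbled cells are visibly corrupt and would prompt a query. *Continue* would not: it is ordinary English, and the hypothyroidism row uses it in its plain sense. A reader of the English copy cannot tell from the cell alone that it is a mistake.

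**Working it through.** No design calculation applies. The check compares the two cells with the rest of section 3.6, counts the wording across the table, and sizes the literal reading.

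**1. Consistency with the surrounding text**

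- *Introductory paragraph.* It names suspension and permanent discontinuation as the adjustments for envafolimab. Continuing through the event is neither.
- *Severity order, skin.* The row for other reactions suspends a first grade 2 or 3 reaction and names dermatitis. Taken literally, grade 2 dermatitis is held while suspected SJS or TEN is dosed through.
- *Next step.* Level 4 is permanent withdrawal in both categories. The literal ladder goes from full dosing straight to permanent withdrawal.
- *Logic.* Suspending until recovery is a usable rule. Continuing until recovery means dosing during toxicity and stopping once the patient is well.

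**2. Count of the table's action cells**

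| Action as printed | Cells |
|---|---|
| Permanent withdrawal | 10 |
| Clear suspend or stop | 6 |
| Literal continue (grade 2 hypothyroidism) | 1 |
| Continue until grade 0-1 (the two at issue) | 2 |
| Garbled, unreadable or self-contradictory | 8 |
| Total | 10 + 6 + 1 + 2 + 8 = 27 |

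The eight are *Sucontinue* (3), *Suuse* (2), *Suused* (1), *cont.rem* (1, injection site reaction level 2) and hypersensitivity level 3-4 (1). The last is not an instruction to keep dosing: it ends in permanent withdrawal, and the milder row already stops the drug.

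Cells that run until grade 0-1: 2 clear suspensions (hyperthyroidism, other reactions) + 5 garbled (*Sucontinue* 3, *Suuse* 2) + 2 *Continue* = 9. The two cells at issue share the sentence form of the *Sucontinue* cells. The hypothyroidism cell has no grade 0-1 condition.

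**3. Other rules that might hold the drug**

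- *Section 4.6* ends treatment for serious adverse events. It covers suspected SJS or TEN if the event is classed as serious. It does not cover a level 3 thrombocytopenia that falls outside the definition in section 3.9.
- *The platelet rule in section 3.6* (count below 50 × 10⁹/L) reduces chemotherapy by 20% at the investigator's discretion and does not address envafolimab.
- *The recurrent or persistent row* acts on recurrence, or on failure to recover within 12 weeks after the last dose. It does not hold the next two-weekly dose for a first event.

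**4. Size on the literal reading**

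Planned doses (section 3.1): 2 induction + 3 with chemoradiotherapy + 2 consolidation = 7, each 200 mg every two weeks.

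- Minimum: one further 200 mg dose, if the event is unresolved when the next dose falls due.
- Maximum: 7 − 1 = 6 further doses, 6 × 200 mg = 1,200 mg, if the event follows dose 1, never resolves and triggers no other stopping rule.

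**The case against.** The strongest reply is that this is a fault of the English copy and not of the plan. The text is visibly a rough translation: the same section has nonsense words in the platelet threshold and the carditis row. The trial runs at one hospital in Yunnan, so the source-language table is probably the working document, and it may already say suspend. Nobody chose to dose through suspected SJS, and an experienced investigator reading the paragraph above the table would hold the drug. The paragraph says suspension may be needed and presents the table as recommendations, so it does not strictly require suspension. The six-dose figure needs an event that never resolves, never worsens to level 4 and is never classed as serious.

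Much of this stands. The word is very probably a mistranslation, the intent can largely be inferred, and the source is not available here. That suspension is required is an inference. It is strongest for the skin row, because dermatitis is named elsewhere. For thrombocytopenia it rests on the introductory paragraph, the parallel rows and the level 4 step. The six-dose figure is a ceiling, not a forecast.

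The reply does not make the printed instruction right. The cells are dosing rules, the printed word is the opposite of the intended one, and no other rule holds envafolimab for a non-serious level 3 thrombocytopenia.

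**Conclusion.** The concern holds. Two of 27 action cells are wrong as written, and each reverses a safety hold; eight more need repair. Confidence is high about the English wording and its conflict with the rest of section 3.6. Whether the working rule at the site is wrong depends on the source-language table.

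The exposure at stake is 200 mg to 1,200 mg of envafolimab per affected patient on the literal reading. The documents give no frequency for these events in this population, so no expected number of patients can be stated. This is a patient-safety correction: nothing here bears on the adverse-event endpoint, the sample size, the error rates or the pCR analysis. It should be fixed.

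**What to change.** 1. Compare the whole envafolimab table with the source-language text, including the unreadable *cont.rem* cell for injection site reaction level 2.
2. Subject to that check, print 'Suspend until adverse effects return to grade 0-1' in the row for grade 3 skin reactions or suspected SJS/TEN and in the level 3 thrombocytopenia row.
3. Print 'Stop immediately and permanently withdraw' for hypersensitivity level 3-4.
4. Replace *Sucontinue*, *Suuse* and *Suused* with 'Suspend'.

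The cost is a corrected table or translation. If the source already says suspend, only the English copy changes. The design and the statistical analysis stay as they are.
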